8.2 Collection and Recording of Adverse Events

8.2.1 AE Collection Methods

All AEs and SAEs occurring during the study period will be captured through the methods described below:

1. **SEC:** Participants will complete an SEC at all in-person visits during the treatment period (including Pre-Quit as a baseline measure) after the Baseline Visit. The SEC will assess the severity of side effects that may be TN related and experienced by participants in the study (See section 7.1: Potential Study Risks; Transdermal Nicotine). These reports will be formally documented as **anticipated (expected)** AEs whether or not the event(s) is ultimately deemed related or not related to the use of TN in this study. The reporting period for each assessment will inquire about any side effects experienced since the last in-person visit. Items will be rated by participants utilizing the following severity scale: 0 (None=No Concerns), 1 (Mild=Side effect does not interfere with usual daily activities), 2 (Moderate= Side effect does interfere with some activities), and 3 (Severe=No normal activities are possible). Any side effect rated **severe or moderate** will require additional follow up per the internal reporting procedures outlined below in section 8.2.2. **Mild skin redness, skin rash, skin swelling, irregular heartbeat, or heart palpitations** also require additional follow up per the internal reporting procedures outlined below in section 8.2.2. Other side effects reported as mild, but not identified above, do **not** require additional follow up from the research staff or communication with the Project Manager, Study Physician, and Principal Investigator. However, these mild reports are maintained within the data management system and are available via aggregate report.
2. **Open-Ended AE Form:** Participants will be asked an open-ended question about any symptom or medical event that may be related to their study participation **not** included on the SEC form at all in-person visits after the Baseline Visit. These events will be

CONFIDENTIAL

This material is the property of the University of Pennsylvania. Do not disclose or use except as authorized in writing by the study sponsor

documented as **unanticipated (unexpected)** AEs unless they are otherwise outlined in the protocol or consent (i.e. related to withdrawal, assessments, etc.). The reporting period for each assessment will inquire about any event(s) or symptom(s) experienced since the last in-person visit. If a participant reports a symptom or medical event, they will be asked to rate the severity of the event utilizing the following severity scale: 0 (None=No Concerns), 1 (Mild=Issue does not interfere with usual daily activities), 2 (Moderate=Issue does interfere with some activities), and 3 (Severe=No normal activities are possible). Any report on the Open-Ended AE Form will require additional follow up per the AE documentation and internal reporting procedures outlined below in section 8.2.2.

3. **Spontaneous Assessment:** Once enrolled, participants will be instructed to inform the research team about any notable symptom or medical event/concern throughout their participation in the study. A participant may also request the Study Physician be consulted about any reported medical event or concern of any severity at any time throughout their participation. At the Pre-Quit Visit (Week -1), participants will receive an emergency medical card (EMC) with the Study Physician's direct contact information should a medical issue or concern that they believe may be related to the study procedures require immediate attention.

An "AE Note" template will be available to the research staff to collect supporting AE information and will function as the source document. However, research staff may collect AE information on any source document available to them and transfer the relevant information to a formal AE Note at a later time. Any notable AE reported spontaneously will require additional follow up per the AE documentation and internal reporting procedures outlined below in section 8.2.2.

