8.1 Definitions

Unanticipated Problems Involving Risk to Subjects or Others:

Any incident, experience, or outcome that meets all of the following criteria:

CONFIDENTIAL

This material is the property of the University of Pennsylvania. Do not disclose or use except as authorized in writing by the study sponsor

- Unexpected in nature, severity, or frequency (i.e. not described in study-related documents such as the IRB-approved protocol or consent form, the investigators brochure, etc.)
- Related or possibly related to participation in the research (i.e. possibly related means there is a reasonable possibility that the incident, experience, or outcome may have been caused by the procedures involved in the research)
- Suggests that the research places subjects or others at greater risk of harm (including physical, psychological, economic, or social harm).

Adverse Event:

An **adverse event** (AE) is any symptom, sign, illness or experience that develops or worsens in severity during the course of the study (regardless if TN related). Intercurrent illnesses or injuries should be regarded as adverse events. Abnormal results of diagnostic procedures are considered to be adverse events if the abnormality:

- results in study withdrawal
- is associated with a serious adverse event
- is associated with clinical signs or symptoms
- leads to additional treatment or to further diagnostic tests
- is considered by the investigator to be of clinical significance

Serious Adverse Event:

Adverse events are classified as serious or non-serious. A **serious adverse event** (SAE) is any AE that is:

- fatal
- life-threatening
- requires or prolongs hospital stay
- results in persistent or significant disability or incapacity
- a congenital anomaly or birth defect
- an important medical event

Important medical events are those that may not be immediately life threatening, but are clearly of major clinical significance. They may jeopardize the subject, and may require intervention to prevent one of the other serious outcomes noted above. For example, drug overdose or abuse, a seizure that did not result in in-patient hospitalization, or intensive treatment of bronchospasm in an emergency department would typically be considered serious.

All adverse events that do not meet any of the criteria for serious should be regarded as **non-serious adverse events**.

Adverse Event Reporting Period:

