The study period during which AEs/SAEs will be reported is from the initiation of any study procedures until the end of the study. Any event(s) that the subject, or the subject's personal physician, believes might reasonably be related to participation in the study after the final time point will be assessed and reported as appropriate.

Preexisting Condition:

A preexisting condition is one that is present at the start of the study. A preexisting condition should be recorded as an adverse event if the frequency, intensity, or the character of the condition worsens during the study period.

Post-study Adverse Event:

CONFIDENTIAL

This material is the property of the University of Pennsylvania. Do not disclose or use except as authorized in writing by the study sponsor

All unresolved adverse events should be followed by the investigator until the events are resolved, the subject is lost to follow-up, or the adverse event is otherwise explained. At the last scheduled visit, the investigator should instruct each subject to report any subsequent event(s) that the subject, or the subject's personal physician, believes might reasonably be related to participation in this study.

Hospitalization, Prolonged Hospitalization or Surgery:

Any AE that results in hospitalization or prolonged hospitalization should be documented and reported as a SAE unless specifically instructed otherwise in this protocol. Any condition responsible for surgery should be documented as an AE if the condition meets the criteria for an AE.

Neither the condition, hospitalization, prolonged hospitalization, nor surgery are reported as an adverse event in the following circumstances:

- Hospitalization or prolonged hospitalization for diagnostic or elective surgical procedures for a preexisting condition. Surgery should **not** be reported as an outcome of an adverse event if the purpose of the surgery was elective or diagnostic and the outcome was uneventful.
- Hospitalization or prolonged hospitalization required to allow efficacy measurement for the study.
- Hospitalization or prolonged hospitalization for therapy of the target disease of the study, unless it is a worsening or increase in frequency of hospital admissions as judged by the clinical investigator.

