- Related to the research study; AND
- When other participants are believed to be at an increased risk of harm

Must be reported to the IRB within 3 days from the time the investigator becomes aware of the death.

Other Reportable events:

For clinical drug trials, the following events are also reportable to the Penn IRB:

- Any adverse experience that, even without detailed analysis, represents a serious unexpected adverse event that is rare in the absence of drug exposure (such as agranulocytosis, hepatic necrosis, Stevens-Johnson syndrome).
- Any adverse event that would cause the sponsor to modify the investigators brochure, protocol or informed consent form, or would prompt other action by the IRB to assure protection of human subjects.
- Information that indicates a change to the risks or potential benefits of the research, in terms of severity or frequency. For example:
 - An interim analysis indicates that participants have a lower rate of response to treatment than initially expected.
 - Safety monitoring indicates that a particular side effect is more severe, or more frequent than initially expected.
 - A paper is published from another study that shows that an arm of your research study is of no therapeutic value.
- Change in FDA safety labeling or withdrawal from marketing of a drug, device, or biologic used in a research protocol.
- Breach of confidentiality
- Change to the protocol taken without prior IRB review to eliminate apparent immediate hazard to a research participant.
- Incarceration of a participant when the research was not previously approved under Subpart C and the investigator believes it is in the best interest of the subject to remain on the study.
- Complaint of a participant when the complaint indicates unexpected risks or the complaint cannot be resolved by the research team.

CONFIDENTIAL

This material is the property of the University of Pennsylvania. Do not disclose or use except as authorized in writing by the study sponsor

- Protocol violation (meaning an accidental or unintentional deviation from the IRB approved protocol) that in the opinion of the investigator placed one or more participants at increased risk, or affects the rights or welfare of subjects.

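### Section 8.2.1 calls the Pre-Quit side-effects checklist a baseline but records checklist reports as AEs without requiring a new or worse symptom, which conflicts with 8.1 for symptoms present at study start and unchanged

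*Combined protocol and SAP*

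**What the plan says.** Section 8.2.1 (item 1) gives the Pre-Quit form a special status: "Participants will complete an SEC at all in-person visits during the treatment period (including Pre-Quit as a baseline measure) after the Baseline Visit". Pre-Quit falls at about week -1 (6.2.4), and patch treatment starts at week 0 (5.2), so this is a pre-patch reading.

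The recording rule in the same item makes no exception for that visit: "These reports will be formally documented as anticipated (expected) AEs whether or not the event(s) is ultimately deemed related or not related". The SEC entry in section 6.5.2 repeats the recording rule, though not the baseline label. The recall window is also in 8.2.1: "The reporting period for each assessment will inquire about any side effects experienced since the last in-person visit". Items are scored 0 to 3 for severity.

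Section 8.1 defines the event differently. An AE "is any symptom, sign, illness or experience that develops or worsens in severity during the course of the study", and "A preexisting condition should be recorded as an adverse event if the frequency, intensity, or the character of the condition worsens during the study period".

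Follow-up depends on grade. Moderate and severe reports, and mild reports of skin redness, rash, swelling, irregular heartbeat or palpitations, go to the 8.2.2 procedure. That procedure collects onset, resolution and possible relation to the patch, and passes earlier reports to the investigator and Study Physician. All other mild reports are kept in the data management system for aggregate reporting, without follow-up.

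**The concern.** A baseline is named and then given no use. No section compares a later score with it, and the form asks about presence and severity, not onset or change. A participant with a steady, long-standing complaint can therefore report it at Pre-Quit and at every later treatment visit, and each report meets the 8.2.1 rule while none meets the 8.1 definition.

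What is at stake is the absolute frequency of side effects. Both arms receive open-label patches (3.1, 5.2), so no patch-free group shows how common these symptoms would be otherwise. The side effects listed for the patch in 7.1 include non-specific ones such as sleep disturbance, nausea and dizziness. Section 8.3.2 lists, as an example of IRB-reportable information, that "Safety monitoring indicates that a particular side effect is more severe, or more frequent than initially expected". A crude count that includes long-standing symptoms is a poor basis for that judgement.

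**Working it through.** The documents state no SEC rate to reproduce, so the main check sets the rules side by side.

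**Test case.** Take a participant with mild sleep trouble that predates Intake and does not change. The SEC items are not listed; I assume that sleep is among them, because 8.2.1 refers to the 7.1 list.

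| Step | Rule | Result |
|---|---|---|
| Is it an AE? | 8.1, AE and preexisting-condition definitions | No: neither new nor worse |
| Reported at Pre-Quit, grade 1 | 8.2.1 recording rule | Documented as an expected AE |
| Reported again at weeks 0, 1, 2, 4, 6, 8 | 8.2.1 recall window and recording rule | Documented again each time |
| Onset or relatedness check? | 8.2.1 and 8.2.2 | None: mild and not a selected item |
| Compared with Pre-Quit? | No rule anywhere | No |

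Such a symptom can be reported on up to seven scheduled forms (eight with Scan 2).

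**Where 8.1 and 8.2.1 do not conflict.** The reporting period in 8.1 opens with the first study procedure, and relation to the patch is not required. A symptom that starts or worsens after Intake but before the first patch is a valid AE. The conflict is confined to symptoms present at study start and unchanged.

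**Two timing limits on any comparison.**
- The Target Quit Day (TQD) form covers the time since Pre-Quit, which is almost wholly before the first patch.
- Patch and cessation begin together: 6.5.1 has participants quit on the morning of that visit. Section 7.1 lists sleep problems, nausea and dizziness as withdrawal symptoms too. A change from Pre-Quit cannot be assigned to the patch alone.

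**Illustration on assumed figures only.** Let b be the share with an unchanged symptom before the patch and t = 0.10 the share of the others who develop it later.
- Crude share reporting = 1 - (1 - b)(1 - t)
- New cases as a share of all participants = (1 - b) × t

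| b | Crude share | New cases |
|---|---|---|
| 5% | 1 - 0.95 × 0.90 = 14.5% | 9.5% |
| 10% | 1 - 0.90 × 0.90 = 19% | 9% |
| 20% | 1 - 0.80 × 0.90 = 28% | 8% |
| 30% | 1 - 0.70 × 0.90 = 37% | 7% |

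The difference in each row is b itself. It assumes that everyone with the prior symptom reports it at least once after the patch starts.

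**The case against.** The best defence is that broad recording, regardless of relatedness, is a cautious choice, and that 8.2.2 supplies the missing comparison. For moderate, severe and selected mild reports, onset, relatedness and earlier reports are all reviewed, so a pre-patch onset would be visible. That much stands, and it would be wrong to say that SEC reports are never compared with anything. But this is case review; no rule removes an unchanged symptom from a count. The cumulative log takes applicable AEs, a term not defined by reference to baseline. The remaining mild items get no review at all.

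It also stands that nothing is lost. Scores are collected at Pre-Quit and at each later treatment visit, so the comparison can be derived at any time.

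A reader might be tempted to go further in three ways that the documents do not support:
- **That every pre-patch report is wrongly called an AE.** Symptoms that are new or worse since the first study procedure qualify under 8.1.
- **That the trial's patch side-effect rates are inflated.** No such rate is defined, and 6.10 contains no safety analysis. The inflation is a risk for aggregate reports, not a stated result.
- **That the IRB trigger will misfire.** Section 8.3.2 gives no expected frequency or threshold and does not tie its example to raw SEC counts.

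**Conclusion.** The point holds in a limited form. For a symptom present at study start and unchanged, the SEC recording rule in 8.2.1 and 6.5.2 produces an AE that 8.1 excludes. This is more than a missing detail: a stated rule gives a wrong count, and the named baseline has no stated role. The exposure is greatest for the mild items without follow-up.

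The size cannot be determined. The table above rests on assumed prevalences and an assumed 10% incidence, with 5% to 30% shown as a range; it indicates direction and scale only. The primary outcomes are untouched, and a comparison of AEs between BAS+ and SC would be affected about equally in both arms. What suffers is the reading of absolute SEC frequencies.

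**What to change.** Keep collecting and storing every SEC report, and leave all follow-up triggers unchanged.

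1. Reconcile 8.2.1 and 6.5.2 with 8.1. State that Pre-Quit scores are the reference, and that a symptom present at study start and unchanged in frequency, intensity and character is not counted as an AE.
2. Add a derived flag in the data management system and tabulate separately:
   - (a) pre-patch reports: all Pre-Quit reports, and TQD reports unless onset was after the first patch;
   - (b) later reports that are new or of higher severity than the worst pre-patch rating, counted once per participant at the worst grade.
3. Label (b) as new or worse since patch start/quit day, not as caused by the patch.

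Group (a) is a separate table, not a deletion: a Pre-Quit report alone does not show whether the symptom predates Intake, and those that began after it remain AEs.

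The cost is protocol wording and one flag on data already collected. There are two small downsides. Worsening in frequency or character at the same grade is not caught by the score and still relies on staff follow-up under 8.1. A mild TQD report with no recorded onset falls into (a) by default, so a symptom that began within hours of the first patch could be placed there.

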Side Effects Checklist (SEC): Participants will complete a SEC at all in-person visits after the Baseline Visit. The SEC will assess the severity of side effects that may be TN related and experienced by participants in the study (See section 7.1: Potential Study Risks; Transdermal Nicotine). These reports will be formally documented as **anticipated (expected)** AEs whether or not the event(s) is ultimately deemed related or not related to the use of TN in this study. The reporting period for each assessment will inquire about any side effects experienced since the last in-person visit. Items will be rated by participants utilizing the following severity scale: 0 (None=No Concerns), 1 (Mild=Side effect does not interfere with usual daily activities), 2 (Moderate= Side effect does interfere with some activities), and 3 (Severe=No normal activities are possible). See section 8.2.1: AE Collection Methods for further details.

Adverse Events Form (Open-Ended AEs): Participants will be asked an open-ended question about any symptom or medical event that may be related to their study participation not included on the SEC form at all in-person visits after the Baseline Visit. These events will be documented as **unanticipated (unexpected)** AEs unless they are otherwise outlined in the protocol and/or consent form (i.e. related to withdrawal, assessments, etc.). The reporting period for each assessment will inquire about any event(s) or symptom(s) experienced since the last in-person visit. If a participant reports a symptom or medical event, they will be asked to rate the severity of the event utilizing the following severity scale: 0 (None=No Concerns), 1 (Mild=Issue does not interfere with usual daily activities), 2 (Moderate=Issue does interfere with some activities), and 3 (Severe=No normal activities are possible). See section 8.2.1: AE Collection Methods for further details.

Carbon Monoxide (CO): **If the PI deems it is safe for the participant and research staff, based upon federal and University COVID-19 guidance**, CO will be measured at the Intake Visit and all subsequent in-person visits to confirm smoking status. The CO monitor is a handheld device that uses a disposable mouthpiece, reports CO in parts per million (ppm), and takes about 3-5 minutes to administer. In order to remain eligible and confirm smoking status at the Intake Visit, a participant must present with a CO greater than or equal to 5 ppm.

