 - None = No concerns
 - Mild = Side effect or issue does not interfere with usual daily activities
 - Moderate = Side effect or issue interferes with some activities
 - Severe = No normal activities are possible
- Relatedness to the study procedures (PI and/or Study Physician):
 - Unrelated = Definitely not related
 - Unlikely = Doubtfully related
 - Possibly = May be related
 - Probably = Likely related
 - Definitely = Related
- Clinical assessment of subject conducted at time of SAE (if appropriate)
- Results of any laboratory tests and/or diagnostic procedures (if appropriate)
- Autopsy findings (if appropriate)
- Concomitant medications and therapies (excluding treatment of event)
- Relevant Medical History (if appropriate)

Internal Reporting Procedures: All relevant follow-up information outlined above (see AE/SAE documentation) concerning applicable AEs, including all information regarding the occurrence of concurrent smoking and TN (if applicable) and previously reported event(s) and/or side effects, will be reported to the Study Coordinator (or other senior personnel), Principal Investigator, and

CONFIDENTIAL

This material is the property of the University of Pennsylvania. Do not disclose or use except as authorized in writing by the study sponsor

Study Physician to determine a course of action (e.g. continue to monitor, reduce medication dose, stop medication), relatedness (causality) to the study, and expectedness (if not already established). This consult will be documented via email. The clinical course of each event will be followed until resolution, stabilization, or until it has been determined that the study treatment or participation is not (or unlikely) to be the cause.

SAEs that are still ongoing at the end of the study period must be followed up to determine the final outcome unless it has been determined that the study treatment or participation is not the cause. Any SAE that occurs after the study period and is considered to be possibly related to the study treatment or study participation should be recorded and reported immediately per this protocol.

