8.3.1 Investigator reporting: notifying NCI and FDA

In adherence with NCI reporting requirements and GCP standards regardless of IND status, the procedures for reporting SAEs (detailed below) suspected/associated with TN to the FDA are as follows:

1. An SAE that is drug-related (reasonable possibility or related) and unexpected will be reported to the FDA within 15 calendar days of discovery of event.
2. An SAE that is drug-related (reasonable possibility or related), unexpected, and life-threatening or fatal will be reported to the FDA within 7 calendar days of discovery of the event.
3. The FDA will be notified of applicable SAE reports via the MedWatch form/system (FDA Form 3500).

The NCI program officer assigned to this trial will be notified of any actions taken by IRB with regard to data safety monitoring.

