8.3.2 Investigator reporting: notifying the Penn IRB

This section describes the requirements for safety reporting by investigators who are Penn faculty, affiliated with a Penn research site, or otherwise responsible for safety reporting to the Penn IRB. The University of Pennsylvania IRB (Penn IRB) requires expedited reporting of those events related to study participation that are unforeseen and indicate that participants or others are at increased risk of harm. The Penn IRB will not acknowledge safety reports or bulk adverse event submissions that do not meet the criteria outlined below. The Penn IRB requires researchers to submit reports of the following problems within 10 working days from the time the investigator becomes aware of the event:

- Any AE (regardless of whether the event is serious or non-serious, on-site or off-site) that occurs any time during or after the research study, which in the opinion of the Principal Investigator and Study Physician is:

Unexpected (An event is “unexpected” when its specificity and severity are not accurately reflected in the protocol-related documents, such as the IRB-approved research protocol, any applicable investigator brochure, and the current IRB-approved informed consent document and other relevant sources of information, such as product labeling and package inserts.)

AND

CONFIDENTIAL

This material is the property of the University of Pennsylvania. Do not disclose or use except as authorized in writing by the study sponsor

Related to the research procedures (According to the Penn IRB standard operating procedures [SOPs], an event is “related to the research procedures” if the event is deemed **probably or definitely related** to the procedures.”)

Reporting Process:

Unanticipated problems posing risks to subjects or others as noted above will be reported to the Penn IRB using the form: “Unanticipated Problems Posing Risks to Subjects or Others Including Reportable Adverse Events” or as a written report of the event (including a description of the event with information regarding its fulfillment of the above criteria, follow-up/resolution and need for revision to consent form and/or other study documentation).

Copies of each report and documentation of IRB notification and receipt will be kept in the Clinical Investigator’s study file.

Reporting Deaths (more rapid reporting requirements):

Deaths that occur during the course of a research study and that are:

- Unexpected; AND

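### SEC reports are labelled expected because of the form used, with no exception for severity or seriousness, so a serious patch reaction first captured there can miss expedited reporting

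*Combined protocol and SAP*

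**What the plan says.** All references are to the combined protocol and SAP.

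- **SEC rule.** Section 8.2.1 says of SEC reports: "These reports will be formally documented as anticipated (expected) AEs". Section 6.5.2 repeats the rule and applies it "whether or not the event(s) is ultimately deemed related or not related to the use of TN in this study". The SEC severity scale runs from 0 to 3, with 3 meaning severe, and neither section makes an exception for any grade or for a serious outcome.
- **Open-ended form.** By contrast, events on the Open-Ended AE Form start as unexpected, with a stated exception for events already covered in the protocol or consent.
- **Definitions.** Section 8.1 describes an unanticipated problem as "Unexpected in nature, severity, or frequency". Section 8.3.2 calls an event unexpected when "its specificity and severity are not accurately reflected in the protocol-related documents", and lists the consent document and the product labelling among the reference sources.
- **Review step.** Under section 8.2.2, moderate, severe and selected mild SEC reports go to senior staff, the Principal Investigator and the Study Physician. They settle the course of action, causality and "expectedness (if not already established").
- **Records.** The AE record in section 8.2.2 has an expectedness item. The SAE Form list has serious status, severity and relatedness, but no expectedness item.
- **FDA reporting.** Section 8.3.1 states: "An SAE that is drug-related (reasonable possibility or related) and unexpected will be reported to the FDA within 15 calendar days". The limit is 7 days if the event is also life-threatening or fatal.
- **IRB reporting.** Section 8.3.2 requires a report within 10 working days for an AE that is both unexpected and related, where related applies "if the event is deemed probably or definitely related". Section 8.1 uses a wider term: "Related or possibly related to participation in the research".

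**The concern.** Expectedness is one of the conditions that decide whether a serious event leaves the site on an expedited timetable. The protocol's definitions make it a property of the event, while the SEC rule makes it a property of the form. An SEC item can fairly be called expected in nature, since the checklist is built around known patch effects. Its severity, frequency or seriousness in one participant cannot be known when the form is designed.

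The SEC is also the instrument aimed at patch reactions, the drug risk this trial names. Section 10.1 gives ongoing data and safety monitoring to the Principal Investigator, Study Physician, research staff and IRB. A report lost because of a data-capture label would therefore weaken one of only a few layers of oversight.

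**Working it through.** No arithmetic applies. The check follows one event through the text: a patch reaction that the participant ticks on the SEC, that meets an SAE criterion, and that is judged drug-related.

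1. **Capture (6.5.2, 8.2.1).** The event is documented as expected. Nothing in either section makes this depend on grade or outcome.
2. **Review (8.2.2).** The event reaches the Principal Investigator and Study Physician, who assign causality. Expectedness is theirs to decide only where it is still open. For an SEC report, step 1 has closed it, and no sentence tells them to reopen it.
3. **SAE Form (8.2.2).** The listed contents do not prompt for expectedness.
4. **Reporting (8.3.1, 8.3.2).** The routes compare as follows.

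| Route | Requires unexpected | Other conditions | Cover if the SEC label stands |
|---|---|---|---|
| FDA, 15 calendar days | yes | SAE, drug-related | none stated |
| FDA, 7 calendar days | yes | SAE, drug-related, life-threatening or fatal | none stated |
| IRB, 10 working days (AE) | yes | probably or definitely related | partial: investigator and physician opinion, and a separate IRB item on side effects proving worse or commoner than foreseen |

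5. **The same event under the definitions.** Sections 8.1 and 8.3.2 ask whether its severity, among other features, is already described. Section 7.1 first describes skin redness, rash or swelling as mild to moderate. Later it gives severe or lasting skin reactions, generalized hives or rash, marked palpitations and allergic symptoms as reasons to contact the study team. A severe skin reaction is thus arguably described already, while one serious enough for hospital admission is open to argument. The definitions call for a judgement, and the SEC rule removes the instruction to make one.
6. **Exposure window.** The SEC is completed from Pre-Quit (week -1) to End of Treatment (week 8). Pre-Quit is a baseline, because section 5.2 starts patches at week 0. Patch reactions can therefore enter through the SEC from week 0 to week 8.

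A severe rating alone does not open the FDA route, which needs an SAE. The gap therefore matters most for serious, drug-related events whose first record is the SEC.

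**The case against.** The strongest reply is that the SEC label is only a recording convention. The opening of section 8.3 points to section 8.1 for definitions, and the IRB test in section 8.3.2 rests on the opinion of the Principal Investigator and Study Physician under its own definition. Moderate and severe SEC reports reach both of them. Hospital admissions are handled as SAEs whatever form first recorded them, and events may also be reported spontaneously, without an automatic label. An SAE is also an AE, so the expectedness item on the AE record may be completed for it.

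Much of this stands, and it rules out several stronger readings that a reader might infer:

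- *That no SAE first seen on the SEC can reach the FDA or the IRB.* The text does not say that the label overrides the definitions in section 8.3. A careful reviewer could apply those definitions, although nothing instructs it.
- *That the IRB would not see these events.* Section 8.3.2 separately makes reportable a side effect that safety monitoring finds worse or more frequent than foreseen, and any AE that would lead to a change in the protocol or consent. Neither item depends on the SEC label.
- *That a severe rash or palpitations must be unexpected because section 7.1 allows only mild to moderate effects.* Section 7.1 goes further, as shown above. The SEC item list, consent form and product labelling are not among the documents reviewed, so no specific event can be classified here.
- *That the differing relatedness thresholds are an error of the same kind.* Section 8.3.2 attributes its threshold to the IRB's own procedures, and section 8.1 defines a different category with an added greater-risk criterion. This is a separate and weaker point.

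None of these replies supplies an instruction to revisit the SEC label, and section 8.3.1 has no counterpart to the IRB's additional items.

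**Conclusion.** The conflict is real and limited. Sections 6.5.2 and 8.2.1 must be reconciled with sections 8.1 and 8.3.2. As written, a serious, drug-related event first captured on the SEC *can* miss the two FDA routes, with no stated fallback, and the 10-working-day IRB route, with partial cover.

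The conclusion assumes that staff follow the SEC sentence and the section 8.2.2 qualifier literally, and that the event would be judged unexpected under the definitions. The documents give no event rates, so the number affected cannot be computed; it is likely to be small. The change is worth making because what is at risk is the timely reporting of serious events.

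As a secondary matter, an unexpected SAE graded possibly related could qualify for the FDA under section 8.3.1 and meet the relatedness part of section 8.1, yet fall below the AE threshold in section 8.3.2. The protocol should say how such an event is handled.

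**What to change.** - In sections 6.5.2 and 8.2.1, make the expected label on SEC reports provisional.
- For any SEC event rated severe or meeting an SAE criterion, have the Principal Investigator and Study Physician judge expectedness under the definitions in sections 8.1 and 8.3.2, and document the judgement.
- In section 8.2.2, state that the qualifier limiting review to events whose expectedness is still open does not apply to these events.
- Add an expectedness item to the SAE Form contents in section 8.2.2.
- Secondary: state how an event that meets the section 8.1 definition of an unanticipated problem, but is graded only possibly related, is reported to the IRB, given the AE threshold in section 8.3.2.

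The cost is protocol wording, one form item, a few more documented judgements and possibly a few more reports. Nothing changes in treatment, visits or analysis.
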